2.2. Endpoints

In Phase 1b, toxicity data for each cohort will be reviewed prior to each dose escalation by a Cohort Review Committee (CRC). The CRC consists of both Investigator site and Sponsor representatives. Investigator site representatives will include the Principal Investigator and any ancillary staff identified by the Principal Investigator. The Sponsor representatives will include the medical monitor and clinical trial manager and other designee. Each CRC meeting will be held after each dose cohort is complete and prior to initiation of the next dose cohort. The CRC will review the complete, pre-defined safety

Investigational Product: IMU-131
Protocol Identifier: IMU.ACS.001
Protocol Version: Protocol Global Amendment #5, 27 September 2023

and immunogenicity dataset from each dose cohort and will determine, with advice from the Principal Oncologist and Clinical Immunologist, the appropriate dose limiting toxicity (DLT) rule (see [Sections 10.1.1](#) and [10.1.2](#) for details) and whether the study will proceed to the next dose cohort. All patients in a dose cohort must have completed chemotherapy cycle 1 (35 days of the study, including 3 doses of IMU-131) prior to the CRC meeting and opening of the next higher dose cohort for enrollment.

Phase 1b endpoints:

- The safety and tolerability of IMU-131 will be evaluated by adverse events (AEs) and laboratory measurements. AEs and laboratory abnormalities will be graded by Common Terminology Criteria for Adverse Events (CTCAE) v4.03;
- The recommended phase 2 dose will be evaluated by safety/tolerability and immunogenicity data for IMU-131 (P467-specific antibodies (IgG) and Her-2-specific antibodies (IgG) titers).

Phase 1b exploratory endpoints:

- Humoral and cellular immunogenicity data will include P467-specific antibodies (IgG) and Her-2-specific antibodies (IgG) in serum samples and vaccine-specific cytokine levels as well as analysis of regulatory and effector T and B cells taken across study visits. As prediction markers of tumor progression initial evaluation (prior first vaccination) of intra-tumor T cells and regulatory cells in tumor biopsies will be performed, when these tests are available at the hospital pathology laboratory.
- Radiographic data will be analyzed descriptively to explore Response Rate and provide information for sample size calculation for the Phase 2 study.

Phase 2 primary efficacy endpoint:

- OS measured from randomization to death due to any cause.

Phase 2 secondary efficacy endpoints:

- PFS measured from randomization to date of earliest progressive disease (PD) based on blinded central review according to RECIST 1.1 criteria, or to date of death from any cause.
- TTP measured from randomization to date of earliest PD based on blinded central review according to RECIST 1.1 criteria.
- DCR measured from randomization as the proportion of patients achieving a confirmed best overall response of complete response (CR), partial response (PR) or stable disease (SD) based on blinded central review according to RECIST 1.1 criteria.
- ORR measured from randomization as the proportion of patients achieving a confirmed best overall response of CR or PR based on blinded central review according to RECIST 1.1 criteria.
- DOR measured from when earliest CR or PR is observed to PD or death due to any cause based on blinded central review according to RECIST 1.1 criteria.

Investigational Product: IMU-131
Protocol Identifier: IMU.ACS.001
Protocol Version: Protocol Global Amendment #5, 27 September 2023

- Percentage CTS measured from randomization as the sum of diameters based on blinded central review according to RECIST 1.1 criteria.

Phase 2 exploratory endpoints:

- Values and changes from randomization in humoral and cellular immunogenicity data including P467-specific antibodies (IgG), Her-2-specific antibodies (IgG), vaccine-specific cytokine levels and regulatory and effector T and B cells.
- Values and changes from randomization in serum prediction markers of tumor progression.
- Values and changes from randomization in Her-2-specific antibodies (IgG) inhibition of in-vitro tumor cell growth.
- Values and changes in intra-tumor T cells and biochemical markers from pre- and post- treatment tumor biopsies.

Phase 2 Safety Endpoints:

- Incidence of treatment-emergent adverse events (TEAEs), Grade 3 / 4 / 5 TEAEs, serious adverse events (SAEs), and TEAEs leading to study treatment discontinuation.
- Incidence of treatment-emergent Grade 3 / 4 clinical laboratory abnormalities.
- Changes and shifts from randomization in clinical laboratory, vital signs, and electrocardiogram (ECG) parameters.
- Change from randomization in ECOG performance grade.
- Concomitant medication use.
- Treatment compliance.

Phase 2 Dose Escalation Primary Endpoint:

- The safety and tolerability of IMU-131 will be evaluated by adverse events (AEs) and laboratory measurements. AEs and laboratory abnormalities will be graded by Common Terminology Criteria for Adverse Events (CTCAE) v5.0 including:
 - Incidence of treatment-emergent adverse events (TEAEs), Grade 3 / 4 / 5 TEAEs, serious adverse events (SAEs), and TEAEs leading to study treatment discontinuation.
 - Incidence of treatment-emergent Grade 3 / 4 clinical laboratory abnormalities.
 - Changes and shifts in clinical laboratory, vital signs, and electrocardiogram (ECG) parameters.

Phase 2 Dose Escalation Secondary Endpoints:

- OS measured from enrollment to death due to any cause.
- PFS measured from enrollment to date of earliest progressive disease (PD) based on Investigator disease assessment according to RECIST 1.1 criteria, or to date of death from any cause.

Investigational Product: IMU-131
Protocol Identifier: IMU.ACS.001
Protocol Version: Protocol Global Amendment #5, 27 September 2023

- TTP measured from enrollment to date of earliest PD based on Investigator disease assessment according to RECIST 1.1 criteria.
- ORR measured from enrollment as the proportion of patients achieving a confirmed best overall response of CR or PR based on Investigator disease assessment according to RECIST 1.1 criteria.
- DOR measured from enrollment to when earliest CR or PR is observed to PD or death due to any cause based on Investigator disease assessment according to RECIST 1.1 criteria.
- DCR measured from enrollment as the proportion of patients achieving a confirmed best overall response of complete response (CR), partial response (PR) or stable disease (SD) based on Investigator disease assessment according to RECIST 1.1 criteria.
- Percentage CTS measured from enrollment as the sum of diameters based on Investigator disease assessment according to RECIST 1.1 criteria.

Phase 2 Dose Escalation Exploratory Endpoints:

- Values and changes from enrollment in humoral and cellular immunogenicity data including P467-specific antibodies (IgG), Her-2-specific antibodies (IgG), vaccine- specific cytokine levels and regulatory and effector T and B cells.
- Values and changes from enrollment in serum and biochemical markers of tumor progression.
- Values and changes from enrollment in Her-2-specific antibodies (IgG) inhibition of in-vitro tumor cell growth.
- Values and changes from enrollment in intra-tumor T cells and biochemical markers from pre- and post- treatment tumor biopsies.

3. STUDY DESIGN

This protocol for patients with HER2/neu overexpressing metastatic or advanced adenocarcinoma of the stomach or GEJ has a 2-part design.

Part 1 consists of Phase 1b: Dose Escalation

Phase 1b is an open-label, single arm, dose escalation study to evaluate safety, tolerability and immunogenicity and to assess the RP2D of IMU-131 initiated 14 days prior to the start of chemotherapy. The first dose cohort will be administered 3 doses of 10 μ g IMU-131, the second dose cohort will be administered 3 doses of 30 μ g IMU-131 and the third dose cohort will be administered 3 doses of 50 μ g IMU-131. All patients entering the Phase 1b study will receive IMU-131 and chemotherapy. RP2D is defined as the dose resulting in the best safety/tolerability and immunology results and will be determined after all dose cohorts have completed Day 56 of the study and an interim analysis of the Phase 1b data has been conducted by the CRC.

Phase 1b follows a standard and well validated dose escalation methodology. Review of toxicity data will be conducted by the CRC as soon as each dose level cohort has completed chemotherapy cycle 1 (35 days of the study, including 3 doses of IMU-131) to ensure

Investigational Product: IMU-131
Protocol Identifier: IMU.ACS.001
Protocol Version: Protocol Global Amendment #5, 27 September 2023

ongoing scrutiny of the IMU-131 safety profile. Phase 1b dose escalation will involve 3 dose levels of IMU-131 within a standard 3+3 scheme for determination of safety prior to dose escalation to next dose cohort. Within the 3+3 scheme if the CRC determines there is no dose-limiting toxicity (DLT) for any of the 3 patients in a dose cohort then only 3 patients will enter this cohort before the next dose cohort is opened to recruitment. However if 1 of 3 patients in a cohort has a DLT event then an additional 3 patients will be enrolled at the existing dose level for further evaluation of this dose by the CRC (see [Section 10.1.2](#) Phase 1b Dose Escalation for full details). If there is a single DLT event in each dose cohort before escalation to the next dose cohort then it is possible for a maximum of 18 patients (6 per dose cohort) to be enrolled in the phase 1b study.

Cohort Expansion and RP2D Definition for Phase 1b Study

Dose cohorts in the phase 1b study will be expanded according to a 3+3 safety evaluation design by CRC decision according to the DLT rules presented in [Section 10.1.2](#). This design allows for up to 6 patients per dose cohort for a maximum of 18 patients enrolled in the study. Alternatively, once 3 patients on a single dose have been reviewed and the CRC has given approval to proceed to the next dose cohort then the previous dose cohort may be expanded up to 5 patients per cohort to allow for more thorough evaluation of safety or immunogenicity. Additional recruitment resulting in up to 5 patients per cohort for further safety and immunogenicity evaluation will be at the Sponsor's discretion.

The open-label conduct of Phase 1b allows for rapid assessment of the drug-relatedness status of any toxicity thereby permitting fast and accurate patient safety evaluation.

[figure not shown]
Phase 1b is a multicenter study with up to 18 patients enrolled. Only 15% - 25% of patients with ACS test positive for HER2/neu over expression, and of these patients it is expected 50% will consent and be eligible for Phase 1b. Thus, approximately 180 patients will be screened for Phase 1b.

A total of 3 injections of IMU-131 (P467-CRM – Montanide emulsion) at the specified dose will be given to patients (on Days 0, 14, and 35), with chemotherapy cycles every 21 days starting from Day 14. Chemotherapy will be ceased by the investigator when clinically indicated for the care of the patient. Patients will be discontinued from the study and cease IMU-131 vaccinations when there is documented evidence of disease progression according to the RECIST 1.1 or if unacceptable toxicity occurs (see [Section 6.5](#) Patient Withdrawal for complete discontinuation criteria).

For a representation of the timeline of events in Phase 1b see [Figure 1: Timeline for Phase 1b](#) and for a flow diagram of Phase 1b see [Appendix 1: Flow Diagram of Phase 1b](#).

Investigational Product: IMU-131
Protocol Identifier: IMU.ACS.001
Protocol Version: Protocol Global Amendment #5, 27 September 2023

Figure 1: Timeline for Phase 1b

Phase 1b Long Term Maintenance

Patients completing the Day 56/End of Treatment Visit for Phase 1b will be maintained on booster doses of IMU-131 starting from Day 98. A Long Term Maintenance visit will occur every 12 weeks and consist of a booster vaccination, a urine pregnancy test, collection of blood samples for hematology, serum chemistry and titer kinetic evaluation, a physical examination including vital signs (BP, pulse and temperature), a radiographic assessment and collection of adverse event and concomitant medication data until the patient is no longer participating in long-term maintenance, or IMU-131 has been shown to be of no clinical benefit, its development is discontinued or the Sponsor decides to terminate the study prematurely. Patients will be discontinued from long term maintenance when there is documented evidence of disease progression according to RECIST 1.1 or if unacceptable toxicity occurs.

For details of the procedures and timing of visits during Long Term Maintenance see [Table 2: Schedule of Activities Long Term Maintenance](#).

Humoral and cellular immunogenicity data will include P467-specific antibodies (IgG) and Her-2- specific antibodies (IgG) in serum samples and vaccine-specific cytokine levels as well as analysis of regulatory and effector T and B cells will continue to be collected when booster vaccinations are given (i.e. every 12 weeks) during long-term maintenance. The dose of booster vaccinations will be determined and vaccination interval confirmed by the titer kinetics evaluated in Phase1b.

Part 2 consists of Phase 2: Evaluation of exploratory clinical activity of IMU-131

Phase 2 will enroll 36 patients and be conducted in the same centers with the addition of new centers, as required, to fulfill recruitment. Phase 2 will have similar inclusion/exclusion criteria and be conducted according to a similar schedule of events and study procedures. During conduct of the Phase 1b study and prior to the start of Phase 2, an amendment to the current protocol will be submitted for ethical and regulatory review. The Phase 2 evaluation of clinical activity of IMU-131 will be initiated after approval of

Investigational Product: IMU-131
Protocol Identifier: IMU.ACS.001
Protocol Version: Protocol Global Amendment #5, 27 September 2023

Phase 2 and upon completion of Phase 1b (all cohorts completed through Day 56 and selection of a RP2D of IMU-131).

[figure not shown]
Phase 2 is an open-label randomized comparison of IMU-131 plus standard of care chemotherapy versus standard of care chemotherapy alone. Patients will be randomly assigned to either 'IMU-131 plus chemotherapy' or 'chemotherapy alone' groups. Treatment for both groups will begin at the Baseline/Day 0 visit.

The IMU-131 plus chemotherapy group will receive vaccination of IMU-131 at Baseline/Day 0, Day 14, Day 35, Day 77, Day 140 and then every 63 days until disease progression. Both the IMU-131 plus chemotherapy group and the chemotherapy alone group will receive chemotherapy starting at the Baseline/Day 0 Visit and then every 21 days for a maximum of 6 cycles as clinically indicated or until disease progression, whichever occurs sooner.

The IDMC will be scheduled to meet after 8, 16 and 24 progression events occur and at intervals no less than once per year. Further details of the IDMC meetings and review procedures will be contained in the IDMC charter.

For a representation of the timeline of events in Phase 2 see [Figure 2: Timeline for Phase 2](#) and for a flow diagram of Phase 2 see [Appendix 6: Flow Diagram of Phase 2](#).

Figure 2: Timeline for Phase 2

Phase 2 Extension

The dose escalation during Phase 2 continues the exploration of clinical activity of IMU-131 and is an open-label, multicenter, single arm dose escalation study with the same inclusion/exclusion criteria as Phase 2 and the same schedule of assessments as Phase 2 IMU-131+chemotherapy arm. The safety of each dose will be assessed by CRC after at least 3 patients have 3 doses of IMU-131 and one cycle of chemotherapy and have completed the 35 day DLT window. Two dose cohorts, consisting of 100µg and 200µg doses of IMU-131, will further characterize the safety, immunogenicity, and clinical activity of IMU-131 in combination with chemotherapy.

Phase 2 dose escalation study will be conducted in Georgia, Serbia, and Ukraine with an approximate duration of 24 months: 15 months for recruitment and approximately 12 months on study.

The Sponsor may close the study once the last patient completes the end of treatment visit.

4. PATIENT STUDY ENROLMENT AND DISCONTINUATION

The following eligibility criteria are designed to select patients for whom protocol treatment is considered appropriate. All relevant medical and non-medical conditions should be taken into consideration when deciding whether this protocol is suitable for a patient.

4.1. Inclusion Criteria

Patients must meet all of the following inclusion criteria to be eligible for enrollment into the study:

1. Patient has been informed of the investigational nature of this study and has given written informed consent in accordance with institutional, local, and national guidelines;
2. Age \geq 20 years old;
3. Life expectancy of at least 12 weeks;
4. **Phase 1b:** No prior chemotherapy or radiotherapy for advanced gastric or GEJ cancer within 6 months prior to Day 0;
5. **Phase 2/Phase 2 Extension:** No prior chemotherapy or radiotherapy for advanced gastric or GEJ cancer within 3 months prior to Day 0;
6. Metastatic gastric or GEJ adenocarcinoma, or locally advanced disease not amenable to surgical resection;
7. HER2/neu overexpression (3+ by immunohistochemistry (IHC) or if IHC 2+ confirmed by fluorescent in situ hybridization [FISH], brightfield double in situ hybridization [BDISH] or chromogenic in situ hybridization [CISH]). Patients with IHC 2+ expression without confirmation of overexpression by fluorescent in situ hybridization [FISH], brightfield double in situ hybridization [BDISH] or chromogenic in situ hybridization [CISH]) may be included in Phase 1b with agreement of Imugene Limited;
8. **Phase 1b:** ECOG performance status 0–1;
9. **Phase 2/Phase 2 Extension:** ECOG performance status 0–2;
10. At least one measurable lesion as defined by RECIST 1.1 criteria. Patients with non-measurable lesions may be included in Phase 1b with agreement of Imugene Limited.;
11. Adequate left ventricular ejection function at baseline, defined as LVEF $> 50\%$ by echocardiogram or MUGA scan (Multi Gated Acquisition Scan);
12. Adequate hematologic function: absolute neutrophil count (ANC) $\geq 1.5 \times 10^9/L$, platelet count $\geq 100 \times 10^9/L$, and hemoglobin $\geq 9 \text{ g/dL}$;
13. Adequate liver function evidenced by bilirubin $\leq 1.5 \times$ laboratory upper limit of normal [ULN], and ALT and AST $\leq 3 \times$ laboratory ULN if no liver involvement or ALT and AST ≤ 5 times laboratory ULN with liver involvement;
14. Adequate renal function (creatinine $\leq 1.5 \times$ laboratory ULN);

Investigational Product: IMU-131
Protocol Identifier: IMU.ACS.001
Protocol Version: Protocol Global Amendment #5, 27 September 2023

15. Willing and able to comply with scheduled visits, treatment plan, laboratory tests, and other study procedures.
16. Male and female patients of childbearing potential must agree to use a highly effective method of contraception throughout the study and for at least 28 days following chemotherapy or 180 days after the last dose of IMU-131 (see [Section 4.3](#) for details). A patient is of childbearing potential if, in the opinion of the investigator, he/she is biologically capable of having children and is sexually active.

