Table 3: Schedule of Activities Phase 2 and Phase 2 Extension

	Screen	Baseline	Week 2 ^K (+/- 3d)	Week 3 (+/- 3d)	Week 5 ^K (+/- 3d)	Week 6 (+/- 3d)	Week 9 (+/- 7d)	Week 11 ^K (+/- 7d)	Week 12 (+/- 7d)	Week 15 (+/- 7d)	Week 18 (+/- 7d)	Week 20 ^K (+/- 7d)	EoT Visit ^O (+/- 7d)	Post-treatment FU Visit ^{Q,R} (+/- 7d)
Study Days	-21d to -1d	0	14	21	35	42	63	77	84 repeat every 84 days (+/- 7d)	105	126 repeat every 84 days (+/- 7d)	140 repeat every 63 days (+/- 7d)	At least 28 (+/- 7) Days after last dose	Every 42 days after EoT
Survival/anti-cancer treatment														X
IMU-131 Vaccination		X	X		X			X					X	
Chemotherapy ^{DF}		X		X		X	X		X	X				
Informed Consent	X													
Demographics and prior medications	X													
Medical History	X													
Cancer History	X													
Physical Exam ^N	X	X		X		X	X		X	X	X		X	
Weight and vital signs (temp, BP, pulse) ^L	X	X	X	X	X	X	X	X	X	X	X	X	X	
Height	X													
ECOG performance status	X	X							X				X	
Radiographic Assessment ^E		X				X			X		X			X ^G
Cardiac Assessment ^H	X								X				X	

Investigational Product: IMU-131
 Protocol Identifier: IMU.ACS.001
 Protocol Version: Protocol Global Amendment #5, 27 September 2023

	Screen	Baseline	Week 2 ^K (+/- 3d)	Week 3 (+/- 3d)	Week 5 ^K (+/- 3d)	Week 6 (+/- 3d)	Week 9 (+/- 7d)	Week 11 ^K (+/- 7d)	Week 12 (+/- 7d)	Week 15 (+/- 7d)	Week 18 (+/- 7d)	Week 20 ^K (+/- 7d)	EoT Visit ^O (+/- 7d)	Post-treatment FU Visit ^{Q,R} (+/- 7d)
Study Days	-21d to -1d	0	14	21	35	42	63	77	84 repeat every 84 days (+/- 7d)	105	126 repeat every 84 days (+/- 7d)	140 repeat every 63 days (+/- 7d)	At least 28 (+/- 7) Days after last dose	Every 42 days after EoT
Tumor biopsy ^I	X								X ^J				X ^J	
Urine Pregnancy Test ^A	X	X	X	X	X	X	X	X	X	X	X	X	X	
HIV, Hepatitis ^M	X													
Hematology, Chemistry ^M	X	X		X		X	X		X	X	X		X	
Exploratory endpoint labs ^B		X							X				X	
Immunology – humoral ^C		X		X		X	X		X		X		X	
Immunology - cellular ^C	X ^P	X							X				X	
Concomitant Medications	X	X	X	X	X	X	X	X	X	X	X	X	X	
Concomitant Procedures	X	X	X	X	X	X	X	X	X	X	X	X	X	
Adverse Events		X	X	X	X	X	X	X	X	X	X	X	X	

Footnotes for Schedule of Activities – Phase 2 and Phase 2 Extension

- A Negative urine pregnancy test required for women of childbearing potential at screening and prior to each vaccination. If positive urine test vaccination may be delayed until negative BHCG blood test.

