4.2. Exclusion Criteria

Patients presenting with any of the following will not be included in the study:

1. Previous treatment with trastuzumab or any other HER2/neu targeting antibody or agent;
2. Continuous systemic treatment with either corticosteroids (>10 mg daily prednisone equivalents) or other immunosuppressive medications within 4 weeks prior to first dose of study treatment. Inhaled or topical steroids and physiological replacement doses of up to 10 mg daily prednisone equivalents are permitted in the absence of active autoimmune disease;
3. Prior organ transplant;
4. **Phase 1b:** Patient not considered a candidate for 5-FU, capecitabine, or cisplatin chemotherapy;
5. **Phase 2/Phase 2 Extension:** Patient not considered a candidate for 5-FU, capecitabine, cisplatin or oxaliplatin chemotherapy;
6. History of documented congestive heart failure; angina pectoris requiring antianginal medication; evidence of transmural infarction on ECG; poorly controlled hypertension; clinically significant valvular heart disease; high risk uncontrolled arrhythmias; or New York Heart Association (NYHA) class II heart disease;
7. If on warfarin (Coumadin®) or other vitamin K antagonists;
8. Concurrent active malignancy except for adequately controlled limited basal cell carcinoma of the skin;
9. Peripheral neuropathy or hearing loss of NCI CTCAE Grade ≥ 2 ;
10. History of uncontrolled seizures, central nervous disorders or psychiatric disability judged by the investigator to be clinically significant and precluding informed consent, participation in the study, or adversely affecting compliance to study drugs;
11. Active infection requiring IV antibiotics;
12. Positive for human immunodeficiency virus (HIV) (HIV 1/2 antibodies) or active hepatitis B (HBsAg reactive) or active hepatitis C (HCV ribonucleic acid [RNA] qualitative) infection;
13. Pregnant or lactating females;
14. Major surgery within 4 weeks prior to study entry. Minor surgery (excluding diagnostic biopsy) within 1 week prior to study entry;

Investigational Product: IMU-131
Protocol Identifier: IMU.ACS.001
Protocol Version: Protocol Global Amendment #5, 27 September 2023

15. Has received a live-virus vaccination within 4 weeks of first study vaccination. Seasonal flu vaccines that do not contain live virus are permitted;
16. Current or recent (within 4 weeks of first IMU-131 vaccination) treatment with another investigational drug or participation in another investigational study.

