4.3. Contraception Guidelines

All male and female patients who, in the opinion of the investigator, are biologically capable of having children and are sexually active, must agree to use a highly effective method of contraception consistently and correctly for the duration of the active treatment period and for at least 28 days following chemotherapy or 180 days after the last dose of IMU-131. The investigator, in consultation with the patient, will select the most appropriate method of contraception for the individual patient from the permitted list of contraception methods, and instruct the patient in its consistent and correct use. The investigator, at each study visit, will confirm and document consistent and correct use. In addition, the investigator will instruct the patient to call immediately if the selected birth control method is discontinued or if pregnancy is known or suspected.

Highly effective methods of contraception are those that, alone or in combination, result in a failure rate of less than 1% per year when used consistently and correctly (ie, perfect use) and include:

1. Established use of oral, injected or implanted hormonal methods of contraception
2. Correctly placed intrauterine device (IUD) or intrauterine system (IUS).
3. Male condom or female condom used WITH a spermicide (ie, foam, gel, film, cream, suppository).
4. Male sterilization with appropriately confirmed absence of sperm in the post-vasectomy ejaculate.
5. Bilateral tubal ligation or bilateral salpingectomy.

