5.2.3. Administration

Chemotherapy is to be administered according to institution standard practice including all pre-medications, concomitant medications and dosing criteria. Dose adjustments and delays, and discontinuation based on AEs, patient's condition, and cumulative toxicities are permitted for the clinical care of the patient at the discretion of the investigator.

Body weight will be determined prior to the start of treatment. Body surface area (BSA: based on weight and baseline height) will be calculated prior to starting each 21-day chemotherapy cycle. Dose modification will be required for $>10\%$ change in BSA, unless investigator considers this not appropriate.

Chemotherapy will be administered in 21-day cycles as tolerated or for any other reason to discontinue chemotherapy treatment as determined by the investigator for the clinical care of the patient.

Phase 1b

IMU-131 administration:

Patients will be enrolled in cohorts of up to 6 patients at one of three escalating dose levels of IMU-131:

- Cohort 1 - $10 \mu\text{g}$ as a 0.1 mL injection
- Cohort 2 - $30 \mu\text{g}$ as a 0.3 mL injection
- Cohort 3 - $50 \mu\text{g}$ as a 0.5 mL injection

The IMU-131 vaccine will be administered IM into the deltoid region of the upper arm with a $0.60 \times 25 \text{ mm}$ 23G needle on Days 0, 14 and 35.

Chemotherapy administration:

Standard of care chemotherapy will be administered as a concomitant treatment to all patients as a 21-day regimen starting 14 days after first IMU-131 vaccination. To document compliance while away from the clinic, patients will record capecitabine treatment in a patient diary.

Chemotherapy will include the following treatments, the dose and duration of which may be varied by the investigator as clinically indicated for the patient: cisplatin, IV (80 mg/m^2 on Day 14, then every 21 days) and either 5-FU, 4000 mg/m^2 as continuous infusion (CIV, administered as $1000 \text{ mg/m}^2/\text{day}$ for 96 hours on days 14 to 17, then every 21 days) or capecitabine for 14 days at $2000 \text{ mg/m}^2/\text{day}$, orally (administered as 1000 mg/m^2 twice daily morning and evening for a total of $2000 \text{ mg/m}^2/\text{day}$ on days 14 to 27, then every 21 days).

Investigational Product: IMU-131
Protocol Identifier: IMU.ACS.001
Protocol Version: Protocol Global Amendment #5, 27 September 2023

Phase 2

IMU-131 administration:

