6.5.3. Additional Discontinuation Criteria

Patients must discontinue from the study if any of the following additional criteria are met:

- The patient requests discontinuation from the study;
- The Sponsor stops the study;
- The Sponsor stops the patient's participation in the study;
- The patient becomes pregnant during the study period.

Investigational Product: IMU-131
Protocol Identifier: IMU.ACS.001
Protocol Version: Protocol Global Amendment #5, 27 September 2023

Patients may withdraw from the study at any time at their own request, or they may be withdrawn at any time at the discretion of the investigator or Sponsor for safety or behavioral reasons, or the inability of the patient to comply with the protocol required schedule of study visits or procedures at a given study site.

If a patient does not return for a scheduled visit, every effort should be made to contact the patient. In any circumstance, every effort should be made to document patient outcome, if possible. The investigator should inquire about the reason for withdrawal, request the patient to return for a final visit, if applicable, and follow-up with the patient regarding any unresolved adverse events (AEs).

If the patient withdraws from the study, and also withdraws consent for disclosure of future information, no further evaluations should be performed, and no additional data should be collected. The Sponsor may retain and continue to use any data collected before such withdrawal of consent.

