8.7. Phase 2/Phase 2 Extension HER2/neu overexpression (Screening)

Confirmation of HER2/neu overexpression is required for inclusion in this study.

A previous pathology result confirming HER2/neu overexpression is acceptable. If analysis of a tumor biopsy is required for confirmation of HER2/neu overexpression, then this may be achieved via analysis of a fresh or archived tissue sample.

HER2/neu analysis will be conducted at each center's local pathology laboratory by immunohistochemistry (IHC) and fluorescent *in situ* hybridization [FISH], brightfield double *in situ* hybridization [BDISH], or chromogenic *in situ* hybridization [CISH] if IHC result is equivocal.

Using the IHC method an unequivocal result of HER2 overexpression is defined as HER2 +++, an equivocal result is defined as HER2 ++, and a negative result is defined as HER2 +. If equivocal result (IHC HER2++) then additional analysis via FISH, BDISH or CISH will be conducted for confirmation of HER2 overexpression. The definition of FISH, BDISH or CISH positivity in gastric or gastro-esophageal junction cancer is a HER2: chromosome 17 ratio of ≥ 2.0 .

8.8. Phase 2/Phase 2 Extension ECOG performance grade (Screening, Baseline, Days 84 then every 84 days and EoT visit)

The ECOG performance grade should be determined using the criteria defined in [Appendix 3: ECOG Performance Status Scale](#).

8.9. Phase 2/Phase 2 Extension Pregnancy Test (at each study visit, excluding post- treatment follow-up visits)

For female patients of childbearing potential, a urine pregnancy test, with sensitivity of at least 25 mIU/mL, will be performed immediately before administration of each vaccine dose. A negative pregnancy test result is required before the patient may receive the investigational product. If urine pregnancy test is positive, then confirmation of pregnancy will be by local laboratory BHCG blood test. If BHCG blood test is negative, then vaccination schedule may resume.

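### The protocol is inconsistent on which women need a negative pregnancy test before IMU-131, and one of its two answers depends on judged sexual activity

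*Protocol*

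**What the plan says.** **Definition.** Protocol Section 4.1, criterion 16 (criterion 14 in the synopsis, same words), reads: "A patient is of childbearing potential if, in the opinion of the investigator, he/she is biologically capable of having children and is sexually active". Neither the protocol nor the SAP defines the term anywhere else. Section 4.3 sets the contraception rule on the same two conditions: "All male and female patients who, in the opinion of the investigator, are biologically capable of having children and are sexually active, must agree".

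**Mandatory negative test.** Section 8.9 and the matching synopsis text say: "For female patients of childbearing potential, a urine pregnancy test, with sensitivity of at least 25 mIU/mL, will be performed immediately before administration" of each dose, and then: "A negative pregnancy test result is required before the patient may receive the investigational product". Table 3 footnote A says: "Negative urine pregnancy test required for women of childbearing potential at screening and prior to each vaccination". Section 7.7 and the footnote to Tables 1 and 2 carry the same limit for Phase 1b, and SAP Appendix 1 repeats the footnote.

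**Visit lists.** Section 6.1 (screening) and the Phase 2/Extension vaccination visits in Sections 6.4.2, 6.4.3, 6.4.5, 6.4.8 and 6.4.12 list a urine pregnancy test marked only as applying to females. At the vaccination visits it comes before the injection in an ordered list. None of these lists says that the result must be negative.

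**Other provisions.** Section 4.2, criterion 13, excludes "Pregnant or lactating females". Section 6.5.3 requires discontinuation if "The patient becomes pregnant during the study period". Section 9.9 bars further IMU-131 doses after a pregnancy.

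**The concern.** Sexual activity is a sensible condition for a promise to use contraception. It is a poor condition for a test whose purpose is to find a pregnancy whatever the patient reports. Because the testing sections borrow a term defined for contraception, the group that must test negative shrinks to women the investigator believes are sexually active. A fertile woman outside that group is also outside the contraception rule, so neither safeguard clearly reaches her.

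The protocol treats pregnancy during vaccination as something to prevent. Discontinuation and the bar on further doses act only once a pregnancy is known, and the test before dosing is the step that would make it known. At stake is whether that step happens at every site for every woman who could be pregnant.

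**Working it through.** No power, alpha or event figure is involved. The check sets the provisions side by side.

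**Step 1: who falls in each group.**
- Section 8.9 and footnote A: female AND of childbearing potential.
- Criterion 16: childbearing potential = biologically capable AND sexually active, both in the investigator's opinion.
- Section 8.9 read with criterion 16: female AND capable AND sexually active.
- Section 6 lists, read literally: female.

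**Step 2: apply both rules to three kinds of woman.**

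| Woman | Section 6 lists, literal | Section 8.9 / footnote A with criterion 16 |
|---|---|---|
| Fertile, judged sexually active | Test listed | Negative test mandatory |
| Fertile, judged not sexually active | Test listed | Not covered |
| Not biologically capable | Test listed | Not covered |

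The rules agree only in the first row. In the second row Section 8.9 is too narrow. In the third row Section 6 tests women who cannot be pregnant. Neither rule picks out exactly the women for whom the test is informative, which is the first two rows together.

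**Step 3: does another provision settle the second row?**
- *Exclusion criterion 13* covers every pregnant woman at entry, but names no test and does not act before later doses.
- *Sections 6.5.3 and 9.9* apply to any woman, but only after the pregnancy is known.
- *Table 3* marks the test at every visit before post-treatment follow-up. The row carries footnote A, so it leads back to the restricted group.
- *Local chemotherapy practice* might include a test, since Section 5.2.3 says "Chemotherapy is to be administered according to institution standard practice including all pre-medications, concomitant medications and dosing criteria". Six cycles every 21 days from Day 0 start on Days 0, 21, 42, 63, 84 and 105. Vaccinations are on Days 0, 14, 35, 77, 140 and then every 63 days. The only shared day is Day 0. The other wording of the Extension schedule (Days 0, 14, 35, then every 63 days, so 35 + 63 = 98, then 98 + 63 = 161) also shares only Day 0.

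**Result.** None of these resolves the disagreement. Whether the woman in the second row is tested depends on which section the site follows.

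**The case against.** The strongest reply is that the visit instructions already test her. At screening and at every Phase 2/Extension vaccination visit, Section 6 lists the test for females without qualification and ahead of the injection, and Section 8.9 does not forbid testing more women than it names. A positive result would have consequences for any woman under exclusion criterion 13 and Sections 6.5.3 and 9.9. The link to criterion 16 is also inferred: the definition sits inside a contraception criterion, covers men as well as women, and is not cited by Sections 7.7 or 8.9.

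Much of this stands, and it is why the point is minor. A reader might infer that a fertile woman judged not sexually active goes through the trial without any pregnancy test. The documents do not support that, because a site following Section 6 as written would test her before each dose.

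Two things remain. The Section 6 lists do not make a negative result a condition for dosing; that rule appears only where the group is restricted. And a site that looks up the term used in Section 8.9 and footnote A will find only one definition, and could reasonably read the marking in Section 6 as shorthand for that group.

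**Conclusion.** The protocol is inconsistent on who must have a negative pregnancy test before IMU-131. On one tenable reading, a fertile woman judged not sexually active may be dosed untested. This conclusion assumes that a site carries the definition in criterion 16 into Section 8.9 and footnote A. No text tells it to do so, but no other definition is offered.

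The size is small. The documents do not give the number of women concerned. It is likely to be low: the Extension, where dosing under the current amendment is planned, enrolls up to 20 patients, men and women, and sites following Section 6 literally already test every woman. No endpoint, analysis or dose-escalation decision is affected. This is a minor correction to a patient-safety rule.

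**What to change.** For pregnancy testing, define childbearing potential by biological capability alone: not postmenopausal and not permanently sterile, with the criteria for each stated. Require a negative test at screening and before each vaccination for every such woman. Use that single term in the Section 6 lists (replacing the bare reference to females), in Section 8.9, in the synopsis and in Table 3 footnote A. Keep sexual activity only as a condition of the contraception undertaking in criterion 16, its synopsis counterpart and Section 4.3.

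The cost is wording in those places and a few urine tests at visits where the test is already scheduled. Women who cannot become pregnant would no longer be listed for testing. No statistical quantity changes.
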